- 16. History or presence of a medical condition or disease that in the Investigator's opinion would place the subject at an unacceptable risk for study participation.
- 17. Participation in any clinical study or having taken any investigational therapy during the 2-month period immediately preceding administration of the first dose of study drug.
- 18. Lactating or pregnant female.
- 19. Women of childbearing potential who do not consent to use highly effective methods of birth control (e.g., sterilisation, or other non-hormonal forms of contraception) during treatment and for at least 12 months after the last administration of study drug. True abstinence periodic abstinence (e.g., calendar ovulation, symptothermal, post-ovulation methods) and withdrawal are not acceptable methods of contraception.
- 20. Subject has been previously randomised in this study.
- 21. Subject likely not to be available to complete all protocol required study visits or procedures.

Treatment Groups and Duration:

The study drug DRL_RI or MabThera[®] will be administered as an i.v infusion, at a dose of 375 mg/m² of BSA. Subjects will receive induction treatment consisting of weekly i.v infusions up to Week 4 followed by maintenance treatment consisting of an i.v infusion every 8 weeks from Week 12 up to Week 36. Subjects will be pre-medicated before each infusion with acetaminophen, diphenhydramine, and 100 mg i.v methylprednisolone or their equivalent to decrease the incidence and severity of acute infusion-related reactions (IRRs).

First Infusion (Day 1): Initiate infusion at a rate of 50 mg/hour. In the absence of infusion toxicity, increase infusion rate by 50 mg/hour increments every 30 minutes, to a maximum of 400 mg/hour.

Subsequent Infusions: Initiate infusion at a rate of 100 mg/hour. In the absence of infusion toxicity, increase rate by 100 mg/hour increments at 30-minute intervals, to a maximum of 400 mg/hour.

Infusions should be administered under close medical supervision. The infusion should be interrupted, or the infusion rate slowed for infusion reactions. If symptoms improve, the infusion rate can be continued at one-half the previous rate.

Whenever the infusion is interrupted, the stop time and restart time should be recorded (with date, hour and minutes) along with initial start and final end time. Rates of infusion throughout should be recorded.

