Infusions should be administered under close medical supervision. The infusion should be interrupted, or the infusion rate slowed for infusion reactions. If symptoms improve the infusion rate can be continued at one-half the previous rate.

The schedule of dosing is presented in Section 1.2.

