6.2.3 Study Drug Administration

Study drug (DRL_RI or MabThera[®]) will be administered by i.v infusion using the escalating infusion rate in accordance with the EMA approved labelling for MabThera[®]. The infusion rate must be well controlled to reduce the incidence of serious IRRs.

Only qualified personnel who are familiar with procedures that minimise undue exposure to them and to the environment should undertake the preparation, handling, and safe disposal of study drugs.

The study drug infusion must be administered in the presence of the Investigator/medically qualified study site staff (to enable compliance), and in an environment where full resuscitation facilities are immediately available. Vital signs will be monitored every 30 minutes during the course of the treatment administration and at the end of infusion or more frequently as necessary.

The study drug will be administered at a dose of 375 mg/m^2 of BSA. Subjects will receive induction treatment consisting of weekly i.v infusions for 4 weeks, followed by maintenance treatment consisting of an i.v infusion every 8 weeks from Week 12 up to Week 36.

The instructions below should be followed in conjunction with the local product labelling if it differs from these instructions. An electronic infusion pump is required to be used.

- First Infusion (Day 1): Initiate infusion at a rate of 50 mg/hour. In the absence of infusion toxicity, increase infusion rate by 50 mg/hour increments every 30 minutes, to a maximum of 400 mg/hour.
- Subsequent Infusions: Initiate infusion at a rate of 100 mg/hour. In the absence of infusion toxicity, increase rate by 100 mg/hour increments at 30-minute intervals, to a maximum of 400 mg/hour.
- Subjects should be closely monitored for the onset of cytokine release syndrome. Subjects who develop evidence of severe reactions, especially severe dyspnoea, bronchospasm or hypoxia should have the infusion interrupted immediately. In all subjects, the infusion should not be restarted until complete resolution of all symptoms, and normalization of laboratory values relating to the infusion reaction. At this time, the infusion can be initially resumed at not more than one-half the previous rate. If the same severe adverse reactions occur for a second time, the decision to stop the treatment should be seriously considered on a case by case basis.

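### The protocol sets two different thresholds for restarting an infusion stopped for a severe reaction, and leaves the scope of the stricter one unclear for milder reactions

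*Protocol*

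**What the plan says.** Three places in the protocol deal with resuming an infusion after a reaction.

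- **Synopsis (Section 1.1, Treatment Groups and Duration).** After telling sites to stop or slow the infusion for a reaction, it adds: "If symptoms improve, the infusion rate can be continued at one-half the previous rate". It then asks for stop and restart times whenever an infusion is interrupted, so restarting is within its scope.
- **Section 6.2.** The action is: "The infusion should be interrupted, or the infusion rate slowed for infusion reactions". The condition for going on is: "If symptoms improve the infusion rate can be continued at one-half the previous rate". No severity grade is attached to either sentence. The only cross-reference there is to Section 1.2, for the dosing schedule.
- **Section 6.2.3.** This section is organised by severity. Its bullet on cytokine release says: "Subjects who develop evidence of severe reactions, especially severe dyspnoea, bronchospasm or hypoxia should have the infusion interrupted immediately". It continues: "In all subjects, the infusion should not be restarted until complete resolution of all symptoms, and normalization of laboratory values relating to the infusion reaction". On the rate it says: "At this time, the infusion can be initially resumed at not more than one-half the previous rate". The following bullet covers mild to moderate reactions. It says that these usually settle when the rate is lowered and that the rate may be raised again as symptoms improve. It is silent on how to restart if such a reaction led to a stop. Ahead of the bullets stands: "The instructions below should be followed in conjunction with the local product labelling if it differs from these instructions".

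The SAP has no restart rule. It summarises infusion-related reactions (Section 4.11.2.10) and dose interruptions (Section 4.11.1) descriptively by treatment group.

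**The concern.** The Synopsis and Section 6.2 each read as complete instructions: dose, infusion-rate schedule and what to do about a reaction. A site working from either has no signal that a stricter restart condition stands elsewhere. Section 6.2.3 can be read as qualifying the general rule, but the protocol does not say so.

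The matter is an acute safety instruction. Section 6.2.3 names dyspnoea, bronchospasm and hypoxia, and Section 6.2.2 notes that acute reactions are seen most often at the first infusion. If sites apply different restart thresholds, a patient's handling during a reaction depends on which text was followed. Interruptions and any recurrent reactions recorded afterwards would then partly reflect site practice. Infusion reactions are a listed safety endpoint and are among the items that the data monitoring committee reviews (SAP Section 4.11.10).

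**Working it through.** No sample size, rate or margin enters this point and the plan gives no figure to reproduce, so the check compares the texts.

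**Step 1: what each text requires**

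| Element | Synopsis and Section 6.2 | Section 6.2.3 |
|---|---|---|
| Reactions covered | Infusion reactions, no severity limit | Severe reactions in one bullet, mild to moderate in the next |
| Action | Stop or slow | Severe: stop at once. Mild to moderate: lower the rate |
| Condition to resume | Symptoms improve | Severe bullet: all symptoms gone and related laboratory values normal. Mild to moderate bullet: none stated for a restart |
| Rate on resuming | One-half the previous rate | Severe bullet: no more than one-half the previous rate |

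The rates are compatible, because exactly one-half satisfies both. The difference lies in the condition.

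**Step 2: apply both texts to the three possible situations**

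1. *Severe reaction, infusion stopped, symptoms improved but still present.* The general rule covers the case because it has no severity limit, and it permits going on at half rate. Section 6.2.3 bars a restart. The thresholds conflict.
2. *Mild or moderate reaction, infusion stopped, symptoms improved but still present.* The general rule permits going on. Whether Section 6.2.3 bars it depends on the first three words of the restart sentence. Taken literally they reach everyone whose infusion was stopped. Taken with the bullet they stand in, they reach only those with a severe reaction. The mild-to-moderate bullet does not settle it. This is an ambiguity of scope.
3. *Reaction handled by slowing only.* Nothing is restarted, and in both texts improvement guides the rate. There is no conflict over restart.

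Situations 1 and 2 assume that continuing at half rate in the general rule includes resuming after a stop. The sentence directly follows one that offers stopping or slowing, so this is the natural reading.

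**Step 3: local labelling.** Section 6.2.3 asks sites to follow its instructions together with the local label where the two differ, but does not say which prevails. No label is among the documents, so whether any label has a different restart condition cannot be checked.

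**Step 4: how many subjects.** The schedule has 4 induction and 4 maintenance infusions (Weeks 12, 20, 28 and 36), so 4 + 4 = 8 per subject. With 312 subjects, 312 × 8 = 2,496 infusions are planned. That is the ceiling on where the rule could be needed. The number affected needs the frequency of reactions that lead to a stop, by severity, and the documents do not give it.

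**The case against.** The best counter-argument is that Section 6.2.3 is the detailed subsection of Section 6.2 and already separates severe from milder reactions, so it simply refines the general rule. The general rule is permissive and the specific one restrictive. A site that obeys Section 6.2.3 breaches nothing in Section 6.2, since symptoms that have gone have also improved. Safeguards apply on either reading: close medical supervision, resuscitation facilities at hand and vital signs every 30 minutes. Stop and restart times and infusion rates are recorded, so variation in practice would be visible.

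Most of this stands, and it limits the point. A reader might infer that sites are told to do opposite things. They are not: both texts allow a stop, and they agree that the resumed rate is not above one-half. What the argument does not remove is that the compatibility runs one way. A site that obeys the Synopsis or Section 6.2 after a severe reaction can breach Section 6.2.3, and nothing on those pages sends it there.

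A reader might also infer that restart conditions differ by country through local labels. The wording leaves that open, but no document shows a label that differs.

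**Conclusion.** The point holds as a contradiction between the general and the specific text for a severe reaction with the infusion stopped, and as unclear scope for a milder reaction with the infusion stopped. It does not extend to reactions handled by slowing.

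The consequence is mainly patient safety at the time of the reaction. Statistically it is small. Allocation is randomised and the staff who give the infusion are blinded, so uneven site practice adds noise to the infusion-reaction and interruption summaries and does not favour an arm. Those summaries are descriptive. No power, margin or primary-analysis figure changes.

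Two larger readings go beyond the documents. One takes the 2,496 planned infusions as the extent of the problem; that figure counts infusions, not reactions. The other carries the effect into the per-protocol set through the 95% to 105% compliance band in SAP Section 4.9. Assuming eight equal doses with one given only in fraction f, overall compliance is (7 + f)/8, which falls below 0.95 when f < 8 × 0.95 − 7 = 0.60. One abandoned infusion could therefore matter for one subject. But the texts differ over when to restart, not over whether the dose is to be completed, and nothing says how often either threshold would lead to an abandoned infusion.

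**What to change.** The passages must be reconciled, and the choice of condition belongs to the sponsor's medical team; this review does not say which is right.

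- State the restart condition once, in Section 6.2.3, and say explicitly which severities it covers, including a mild or moderate reaction for which the infusion was stopped.
- Replace the sentences on continuing in the Synopsis and Section 6.2 with a cross-reference to Section 6.2.3.
- Clarify how the instruction on local labelling applies, and which text prevails if they differ.
- Send the clarified text to all sites.

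The cost is wording in three places, by clarification letter or amendment. No new procedures, data collection or analyses are needed.

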6.2.1 Study Drug Infusion Preparation

Study drug (DRL_RI or MabThera[®]) solutions for infusion will be prepared by an unblinded pharmacist/authorised designee/unblinded qualified physician in this study. Unblinded pharmacist/authorised designee/unblinded qualified physician should use aseptic techniques appropriate to parenteral administration products.

Study drug will be administered by i.v infusion by blinded study personnel. Study drug vials and prepared solutions should be inspected visually for particulate matter and discoloration prior to administration. Do not use vials if particulates or discoloration are present.

6.2.2 **Pre-Medication for Study Drug Infusions**

All subjects should receive pre-medication with 100 mg i.v methylprednisolone or their equivalent to be completed at least 30 minutes prior to rituximab infusions to decrease the incidence rate and severity of acute IRRs. Pre-medication consisting of an anti-pyretic and an antihistamine (e.g., paracetamol [acetaminophen] and diphenhydramine), should always be administered before each infusion of rituximab.

Acute IRRs are most often observed during the first infusion of rituximab. Any reduction in use of pre-medications during subsequent infusions must be in compliance with local labelling and regulation.

6.2.3 Study Drug Administration

Study drug (DRL_RI or MabThera[®]) will be administered by i.v infusion using the escalating infusion rate in accordance with the EMA approved labelling for MabThera[®]. The infusion rate must be well controlled to reduce the incidence of serious IRRs.

Only qualified personnel who are familiar with procedures that minimise undue exposure to them and to the environment should undertake the preparation, handling, and safe disposal of study drugs.

The study drug infusion must be administered in the presence of the Investigator/medically qualified study site staff (to enable compliance), and in an environment where full resuscitation facilities are immediately available. Vital signs will be monitored every 30 minutes during the course of the treatment administration and at the end of infusion or more frequently as necessary.

The study drug will be administered at a dose of 375 mg/m^2 of BSA. Subjects will receive induction treatment consisting of weekly i.v infusions for 4 weeks, followed by maintenance treatment consisting of an i.v infusion every 8 weeks from Week 12 up to Week 36.

The instructions below should be followed in conjunction with the local product labelling if it differs from these instructions. An electronic infusion pump is required to be used.

- First Infusion (Day 1): Initiate infusion at a rate of 50 mg/hour. In the absence of infusion toxicity, increase infusion rate by 50 mg/hour increments every 30 minutes, to a maximum of 400 mg/hour.
- Subsequent Infusions: Initiate infusion at a rate of 100 mg/hour. In the absence of infusion toxicity, increase rate by 100 mg/hour increments at 30-minute intervals, to a maximum of 400 mg/hour.
- Subjects should be closely monitored for the onset of cytokine release syndrome. Subjects who develop evidence of severe reactions, especially severe dyspnoea, bronchospasm or hypoxia should have the infusion interrupted immediately. In all subjects, the infusion should not be restarted until complete resolution of all symptoms, and normalization of laboratory values relating to the infusion reaction. At this time, the infusion can be initially resumed at not more than one-half the previous rate. If the same severe adverse reactions occur for a second time, the decision to stop the treatment should be seriously considered on a case by case basis.
- Mild to moderate IRRs usually respond to a reduction in the rate of infusion. The infusion rate may be increased upon improvement of symptoms.

Medication errors may result in this study from the administration of the wrong drug, by the wrong subject, at the wrong time, or at the wrong dosage strength.

Medication errors are reportable irrespective of the presence of an associated AE/SAE, including:

- Medication errors involving subject exposure to the study drug;
- Potential medication errors or uses outside of what is foreseen in the protocol that do or do not involve the participating subject.

Whether or not the medication error is accompanied by an AE, as determined by the Investigator, medication error should be captured on the medication error section of the AE page and, if applicable, any associated AE(s) captured on an AE eCRF page. All medication errors should be reported to the Sponsor's designated safety services and MM within 24 hours of awareness as described in Section 8.4.2. Expedited reporting of medication error/infusion error to regulatory authorities will be based on the local regulatory requirements.

Whenever the infusion is interrupted, the stop time and restart time should be recorded (with date, hour and minutes) along with initial start and final end time. Rates of infusion throughout should be recorded.

6.3 Preparation/Handling/Storage/Accountability

6.3.1 Packaging

DRL_RI and MabThera[®] will be supplied as sterile, preservative-free, non-pyrogenic, single-use vials CCI

Each vial of DRL_RI will contain 100 mg unit dose of DRL_RI in 10 mL single-use vial or 500 mg unit dose of DRL_RI in 50 mL single-use vial.

Each vial of MabThera[®] will contain 100 mg unit dose of MabThera[®] in 10 mL single-use vial or 500 mg unit dose of MabThera[®] in 50 mL single-use vial.

These rituximab concentrates for solution for infusion will be supplied packaged as blinded supplies in the external packaging (carton) for all products identified with a unique container number. The external packaging (carton) of DRL_RI 100 mg/10 mL and MabThera[®] 100 mg/10 mL will appear identical. Similarly, the external packaging (carton) of DRL_RI 500 mg/50 mL and MabThera[®] 500 mg/50 mL will appear identical.

Each blinded carton will contain 1 vial of study medication, either DRL_RI 100 mg/10 mL or MabThera[®] 100 mg/10 mL for the 10 mL vial size, or either DRL_RI 500 mg/50 mL or

MabThera[®] 500 mg/50 mL for the 50 mL vial size. Each carton will be packaged with a tamperresistant seal. The Sponsor/designee must be notified of any study medication in which the tamperresistant seal has been broken and this medication should not be used.

6.3.2 Labelling

Medication labels will comply with the legal requirements of each country and be printed in the local language (where applicable). They will not disclose the unblinded study drug information.

6.3.3 Storage

All drug supplies for this study must be stored according to labelled storage conditions (2°C to 8°C). The Investigator, or an approved representative (e.g., unblinded pharmacist), will ensure that all study drug is stored in a secured (locked) area with restricted access, and in accordance with applicable regulatory requirements.

Drug should be stored in accordance with the drug label. Investigators and study site staff are reminded to check and record minimum and maximum temperatures daily (i.e., manually or by using alarm systems to alert of any excursions) and ensure that refrigerators and thermometers (periodically validated) and are working correctly as required for proper storage of study drugs. Any temperature excursions should be reported to the Sponsor/designee immediately.

The study drugs must be stored as indicated. Deviations from the storage requirements, including any actions taken, must be documented and reported to the Sponsor/designee immediately. Once a deviation is identified, the study drug must be quarantined and not used until the Sponsor/designee provides documentation of permission to use the study drug.

6.4 Measures to Minimise Bias: Randomisation and Blinding

A double-blind design is employed so that both the Investigators and the subjects will be unaware of the treatment assignment during the whole study.

After written informed consent is obtained from an eligible subject, a unique subject number will be assigned to this subject. This number will be created and allocated by the IWRS, when the subject first enters the system at Screening.

The randomisation codes will be computer-generated and kept by a statistician independent from the project team. Randomisation will be stratified by low, medium, and high-risk subjects using CCI (CCI (CCI), as well as by tumour grade (1-2 Vs. 3a) and geographical area (USA, Europe and Asia-Pacific region).

Randomisation methods will be fully described in the Randomisation Plan specification document.

Subjects who are eligible for randomisation will be assigned a unique randomisation number at the Baseline (Day 0 to Day 1) Visit by IWRS. This randomisation number identifies which treatment will be allocated to the subject and will be used to identify randomised subjects during the study. Subjects who withdraw after randomisation are not to be replaced and their randomisation number will not be re-used.

Dispensing of study drug will be coordinated by IWRS. The system will assign study drug corresponding to the randomisation arm. Due to the study drug not being identical in appearance, methods to maintain the blind of the study drug during dispensing and administration will be employed.

6.4.1 **Procedure for Unblinding**

The study site Investigator and appropriate project team members will be authorised to access the emergency unblinding functionality within the IWRS. The system will require the user to confirm if it is medically necessary to break the randomisation code to complete the emergency unblinding transaction.

The exact description of the treatment assigned to the individual subject then will be accessible. Emergency unblinding can thus be made for any subject without affecting the double-blind nature of the study. Subject treatment information may only be accessed in the event of an emergency and out of necessity to know the identity of the allocated study drug in order to institute appropriate therapeutic management. Should a situation arise where unblinding is urgently required (i.e. knowledge of treatment code is required to adequately manage a life-threatening situation), the Investigator at that study site may perform immediate unblinding through IWRS. If time allows, the Investigator may contact the Sponsor designee MM prior to unblinding the individual subject to discuss the rationale for emergency unblinding.

In the event that emergency unblinding is performed, the Investigator can view and must print the unblinded confirmation document from IWRS. The Investigator must record on the confirmation document printout the reason for the emergency unblinding and sign the document. The confirmation document must then be kept in a safe place until the end of the study. Once a randomisation code has been broken for a subject, he/she must be withdrawn from the study. The Investigator must inform the Sponsor designee MM in writing within 24 hours. An SAE form should be completed and reported in accordance with Section 8.4.2.

